6.3 Missing Data

For dates, year and month are required. If day is missing, it will be imputed to be the 15th of the month. Otherwise, missing values will not be imputed for descriptive statistics or analyses unless otherwise specified.

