11.1.2 Adverse Events

AE reporting is described in [Protocol Section 6](#). Volunteered, observed, and elicited AEs will be recorded in the CRF from the day the ICF is signed through 120 days after the last implant, and in a registry for the rest of each subject's life. This will include AEs subjects report spontaneously, AEs observed by the investigator, and AEs subjects report in response to open-ended questions. AEs will be coded using MedDRA® (Medical Dictionary for Regulatory Activities) version 10.1 (released by MedDRA MSCO SEP 2007) or higher. In MedDRA, each reported event is mapped to a Lowest Level Term (LLT), a Preferred Term (PT), and a System Organ Class (SOC). LLTs constitute the lowest level of terminology and can accommodate colloquial or culturally unique terms. Each LLT is linked to only one PT. A PT is a distinct descriptor for a symptom, sign, disease, diagnosis, therapeutic indication, investigation, surgical or medical procedure, or medical, social or family history characteristic; it groups together equivalent LLTs. A PT must be linked to at least one SOC but can be linked to as many SOCs as appropriate. SOCs provide the broadest level of data retrieval and comprise groupings by etiology, manifestation site, and purpose. Coding will be done by DM using a computer algorithm for exact matches or manual coding for incomplete or non-matches. All coding will be reviewed by a second member of the DM team. The Medical Monitor will review and approve the final coding prior to database lock.

A treatment-emergent AE (TEAE) will be defined as an AE that began or worsened during or after the first implantation and within 120 days after the last implantation. AEs recorded prior to the first implantation will be considered non-treatment-emergent. AEs with no recorded start date will be considered treatment-emergent, as will AEs with no recorded start time that began on the same day as the first implantation. All AEs will be listed, but only TEAEs will be summarized and analyzed.

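### An adverse event with no onset day, in the same month as a first implant done after the 15th, is dated before the implant and drops out of the TEAE summaries

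*SAP*

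**What the plan says.** SAP 6.3 (Missing Data) sets one rule for all dates: "For dates, year and month are required", and "If day is missing, it will be imputed to be the 15th of the month". It names no exception and sets no floor at the implant date.

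SAP 11.1.2 defines a TEAE as "an AE that began or worsened during or after the first implantation and within 120 days after the last implantation". It adds that "AEs recorded prior to the first implantation will be considered non-treatment-emergent", and that "All AEs will be listed, but only TEAEs will be summarized and analyzed". Two gaps in the onset record are resolved in favour of counting the event: "AEs with no recorded start date will be considered treatment-emergent, as will AEs with no recorded start time" if they began on the day of the first implant. An onset with month and year but no day is not mentioned. AEs are "recorded in the CRF from the day the ICF is signed through 120 days after the last implant", so events before and after the implant can share a calendar month.

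Other defaults in the SAP are conservative. In 11.1.2, missing severity counts as severe and missing relationship as probably related. In section 9, a medication whose exposure cannot be determined from partial dates counts as concomitant. SAP 6.1 shows partial dates in listings as recorded.

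**The concern.** The TEAE definition turns on when an event began relative to the first implant. When the day is missing, the only onset date the SAP supplies is the one from 6.3, and that rule takes no account of the implant date. An event known to fall in the implant month can therefore be excluded, while one with no date at all is included: more information leads to less conservative handling.

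The exposed events are those soon after the first surgery. The outputs at stake are the TEAE tables by SOC, preferred term, severity and relationship, the frequently reported events, the treatment-emergent SAE table (14.3.2), and the two listings that SAP 16.1 restricts by title to treatment-emergent events (leading to discontinuation and to death). The groups are small. If the lost event is a subject's only occurrence of a term, that incidence falls by 1/10 = 10 percentage points with the 10 pancreatic subjects of SAP 3.2, or 1/40 = 2.5 points with the 40 of protocol Appendix 3.

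A smaller issue has the same cause: a death with the day missing could be placed before a documented contact, or before the implant.

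**Working it through.** The documents give no figure to reproduce, so this is a check of date logic followed by a size calculation.

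**1. When the rule misfires.** Let the first implant fall on day d of its month, with true onset on or after it and the day missing.
- Same month, d > 15: imputed day 15 < d, so onset always precedes the implant. Example: implant on the 20th, onset on the 22nd, imputed to the 15th, 5 days before the implant.
- Same month, d ≤ 15: 15 ≥ d, so the event is kept.
- Later month: the 15th of a later month always follows the implant, so the event is kept.

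Enumerating 3 years of implant dates (1,096 dates, 556 of them after the 15th, 50.7%) with onset on days 0 to 120 confirms this. For implants after the 15th, 4,583 of 4,583 same-month combinations are misclassified and 0 of 62,693 later-month combinations are.

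**2. Share of same-month post-implant events lost.** Assume a 30-day month, every implant day equally likely, and onset equally likely on each permitted day after the implant.

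| Onset window | Lost (d > 15) | All | Share |
|---|---|---|---|
| Rest of month | 14+13+…+1 = 105 | 29+28+…+1 = 435 | 24.1% |
| Within 7 days | 8×7 + 21 = 77 | 23×7 + 21 = 182 | 42.3% |
| Within 3 days | 12×3 + 3 = 39 | 27×3 + 3 = 84 | 46.4% |

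**3. Share of all day-missing post-implant events lost.** Same enumeration, implant day included, implant dates even over the calendar, missingness independent of date, no later worsening.
- Uniform onset, days 0–120: 4,583 / (1,096 × 121) = 4,583 / 132,616 = 3.5%.
- Uniform onset, days 0–390 (roughly four implants 90 days apart plus the final window, 3×90 + 120): 4,583 / (1,096 × 391) = 4,583 / 428,536 = 1.1%.
- Front-loaded onset, weight exp(−k/14) on day k, days 0–120: 21.1%. The 14-day mean is an assumption, not a figure from the documents.

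**4. Upper limit.** With one implant and uniform onset over days 0–120, about 2.9% of day-missing events have an imputed onset beyond day 120 and are lost there.

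**5. The opposite error.** For implants on or before the 15th, the rule moves some pre-implant events to after the implant. Of day-missing events from the 28 days before the implant, about 12% become TEAEs under the current rule. Classing every day-missing event in the implant month as treatment-emergent raises this to about 52%, before other data are used to exclude any.

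**The case against.** The strongest reply is that the SAP never expressly says the imputed date sets the TEAE flag. Section 11.1.2 speaks of events recorded, not begun, before the first implant, and an event first written down after surgery is not literally in that class. It also declines to compute duration from partial dates, so imputation does not feed every AE derivation. This stands as a reason for less than full certainty. It does not remove the problem: the definition depends on when the event began, 6.3 is the only rule that dates it, and because the duration sentence separates missing from partial dates, the protection for events with no start date does not naturally extend to a known month and year.

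Safeguards also count. SAP 1.1 provides for queries on missing data and edit checks for incomplete or illogical values, and the SAP schedule reviews AEs at Day 0 and Day 14. Peri-operative events without a day should be uncommon, and an illogical death date should usually be queried.

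A reader might infer more than the documents support:
- *That every first implant after the 15th is a problem.* Onset must also fall in that same month, with only the day missing. An event that worsened after the implant remains a TEAE.
- *That the event vanishes from all safety output.* It stays in the full AE listing with its partial date. Deaths have a separate summary with no stated TEAE restriction. The laboratory, vital-sign, ECG and physical-examination tables do not use the flag.
- *That 24–46% of partially dated events are lost.* Those figures apply only to same-month events.
- *That 6.3 and 11.1.2 contradict each other.* They cover different cases; the fault is a gap and an inconsistency of approach.
- *That safety is understated on balance.* The opposite error in step 5 exists, and the net direction is not shown.

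**Conclusion.** The point holds in this limited form. On the natural reading, a true post-implant event with a missing onset day, in the month of a first implant done after the 15th, is always classed as non-treatment-emergent. This is a stated rule that gives a wrong classification, and it runs against the SAP's own conservative defaults.

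The size is conditional. The documents do not say how many onset dates lack a day, so no count of lost events can be given. The percentages rest on implant dates spread evenly over the calendar and on the assumed onset patterns; the front-loaded figure depends directly on the 14-day mean. All analyses are exploratory, so no test is affected; what is affected is the accuracy of the TEAE incidence estimates. The death-date issue is logical only, with no frequency claimed. Living subjects are censored at the time of analysis (SAP 10.1.1), so last contact does not enter as a censoring date.

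**What to change.** In SAP 6.3 and 11.1.2, state that:
- the imputed onset date is used for the TEAE classification;
- an AE with a missing onset day in the month of the first implant is treatment-emergent, with onset imputed to the later of the 15th and the implant date, unless other data (such as an end date or a pre-implant record) show that it began before the implant without later worsening;
- the same principle applies in the month containing day 120 after the last implant: the event counts unless other data show that it began after the limit;
- a death with the day missing is dated to the later of the 15th and the last documented contact, within the recorded month.

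The cost is a few sentences and no new data. True post-implant events lost at the first-implant boundary fall to zero. The downside is that more pre-implant events count as TEAEs: up to about 52% of day-missing events from the 28 days before the implant, against about 12% now. That is the direction the SAP already takes for other missing AE fields. Reporting how many TEAEs were classified on an imputed date would let readers judge the effect.

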6.4 Visit Windows

6.4.1 Study time points

The following study time points are critical in terms of screening procedures, implantation and study termination. Study time point labels correspond to those that are used in the protocol (minus visit numbers) and that will be used in listings and tables. A complete description of all study time points is contained in the Schedule of Assessments ([Section 4](#)). Study visit labels in the Schedule of Assessments differ somewhat from those that are used in the text of the protocol and in the SAP (see samples below):

SAP	Text of Protocol	Schedule of Assessments
Implant 2 / Day 0	Visit 6 / Implant 2 / Day 0	Visit 6 / Implant 2
Implant 3 / Day 0	Visit 11 / Implant 3 / Day 0	Visit 11 / Implant 3
Implant 4 / Day 0	Visit 16 / Implant 4 / Day 0	Visit 16 / Implant 4

In the time-to-death analyses, the time of origin (T_0) will be defined separately for each analysis:

- Time from first scan showing disease progression after completion of prior treatment to death (primary analysis)
- Time from first implantation to death (secondary analysis)
- Time from diagnosis of Stage IV disease to death (secondary analysis)

6.4.1.1 Screening

Screening will occur after the ICF has been signed and within 28 days of the first implantation. Subjects will undergo all screening procedures during this time.

6.4.1.2 Baseline

Individual baselines will be established for each implant. For a given parameter, baseline for each implant will be the last recorded observation prior to the implant.

6.4.1.3 Implant 1 / Study Day 0

The day of the first implant will be designated as Implant 1 / Study Day 0.

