7.2 Determination of Response

All subjects will be evaluated for response. The Evaluation Team will be composed of the Investigators, and one outside physician. All of the clinical tests will be evaluated independently by each member of the Team for changes against the baseline findings. This evaluation will take place prior to each implantation or when the subject leaves the study. The individual subject's baseline established prior to the first implantation will be used for the entire study. A table will be constructed using the changes from baseline.

Outline of Response Rate				
TESTS	Baseline Prior to First Implantation	Results Prior to Second Implantation	Results Prior to Third Implantation	Results Prior to Fourth Implantation
Clinical Findings				
Symptoms				
Global Clinical Assessment				
Quality of Life				
Clinical Laboratory Tests (Abnormalities)				
Tumor Markers (Decrease)				
Imaging Studies (Evidence of Change, e.g., volume or area)				
CT				
PET				
MRI				
Rating Scale				
Major Improvement: 3				
Improvement: 2				
No Change: 1				

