10.1.2 Changes in tumor size and state

All available measurements will be obtained from various radiological assessments

If available, the volume of all measureable lesions will be calculated as length x width x height. Observed values and changes from baseline in relationship to both first and most recent implant will be listed for each study time point at which these data are recorded. For continuous parameters, at each time point, observed values and changes from baseline will be summarized. Nominal outcomes will be categorized and summarized as frequencies and percentages of subjects at each time point. In listings, all available measurements of all lesions and malignant lymph nodes will be shown. For summaries, mean longest diameters, volumes, and densities for a given lesion / node class (e.g., target) for each subject will be calculated and summarized, if available and feasible.

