10.1.3 Change in tumor markers and other biochemical parameters

See [Section 11.1.3](#) below for details on laboratory data collection and reporting. Clinical laboratory parameters will include the tumor markers CEA and CA 19-9. A tumor marker response is defined as a $\geq 20\%$ decrease from baseline in one or both of CEA or CA 19-9.

Other biochemical parameters include:

- Serum enzymes and proteins
- Kidney function (creatinine, blood urea nitrogen (BUN))
- C-reactive protein
- Hematology (leukocytes, hemoglobin, differential, platelets, erythrocyte sedimentation rate (ESR))
- Cytokines
- Cellular and humoral immunity status (observed values will be clinically reviewed to determine presence / absence of each antibody, etc.)
- CA125 is included as part of the assessment of inflammatory response to macrobead placement.

Along with listings and summaries, graphical displays of individual subject observed values over time will be produced for tumor markers, CA125, C-reactive protein, and ESR.

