10.1.4 Clinician and self-rating scales

Clinician and patient self-rating scales will be recorded in the CRF. Observed values and changes from baseline in relationship to both first and most recent implant will be listed for each study time point at which these data are recorded. For continuous or discrete outcomes, observed values and changes from baseline will be summarized at each time point. Nominal outcomes will be categorized and summarized as frequencies and percentages of subjects at each time point. Each rating scale to be evaluated is described below.

10.1.4.1 *Global Clinical Assessment (GCA)*

The GCA is done by the clinician and measures patient clinical status via a visual analog scale (VAS). GCA will be reported as the distance from the left endpoint to the clinician's mark divided by the total length of the horizontal line being marked.

10.1.4.2 *Activities of daily living (ADL) rating / Karnofsky performance status (KPS) scale*

ADL / KPS is a self-rated scale that measures the patient's ability to perform daily functions, ranging from 0 ("dead") to 100 ("normal, no complaints, no evidence of disease").

10.1.4.3 *Quality of life scale / EORTC QLQ-C30*

Quality of life will be assessed using the European Organisation for Research and Treatment in Cancer (EORTC) Quality of Life Questionnaire (QLQ)-C30 version 3.0 ([Aaronson et al. 1993](#)) which uses discretely-scaled responses to 30 questions to derive global health status / quality of life, functionality and symptom scales. The raw data will be used to calculate the derived scales using the EORTC QLQ-C30 Scoring Manual ([Fayers et al. 2001](#)). Per the manual, any derived scale for which more than half of the individual questions that comprise the scale are missing will be set to missing; otherwise, missing values will be ignored (which has the same effect as imputing the average response among non-missing questions that comprise the scale).

10.1.4.4 *Pain scale*

Subjects will be asked to rate their pain on a discrete scale (from 0 = "no pain" to 10 = "worst pain imaginable, unbearable"). Specific anatomical locations of pain will also be recorded.

10.1.4.5 *Eastern Cooperative Oncology Group (ECOG) performance status*

The ECOG Performance Status is used by clinicians to assess disease progression and how the disease is affecting the daily living abilities of the patient; it is scaled as follows:

Status	Description

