11.1.3 Clinical laboratory evaluations

Hematology, coagulation, serum chemistry, serum pregnancy, urinalysis, immunology, immunophenotyping, and all other laboratory parameters including those listed in [Protocol Section 5.6](#) will be analyzed at multiple laboratory sites and will be delivered via hard-copy reports to the central data processing center (VSI). Laboratory test names and units of measurement will be standardized by VSI. For select parameters, study day, collection lab, date and time collected, normal range, observed value, change from baseline in relationship to both first and most recent implant, out-of-range flag, and Common Terminology Criteria for Adverse Events (CTCAE) v3.0 toxicity grade (if applicable) will be listed. Laboratory observations with Grade 3 or higher toxicity and/or reported as an AE will be listed. For all parameters, study day, date collected, observed value, normal range, and out-of-range flag will be output to a spreadsheet. For select parameters, observed values and changes from baseline (in relationship to both first and most recent implant) will be summarized for each time point at which laboratory data were collected. Separate series of tables will show numbers and percentages of subjects by out-of-range flag and by toxicity grade. Shift tables will be provided that show numbers and percentages of subjects with normal ↔ abnormal shifts based on out-of-range flags and/or toxicity grades from baseline (in relationship to both first and most recent implant) to each subsequent time point at which laboratory data are collected.

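### The SAP's marker response and its tumor-size and rating-scale summaries name no baseline, so they default to a per-implant baseline, whereas Protocol 7.2 keeps the one set before the first implant

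*SAP*

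**What the plan says.** Protocol 7.2, on the evaluation of response, says that the individual subject's "baseline established prior to the first implantation will be used for the entire study". Its response table has one baseline column, followed by results before implants 2, 3 and 4.

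SAP 6.4.1.2 says "Individual baselines will be established for each implant" and that "baseline for each implant will be the last recorded observation prior to the implant". SAP sections 1 and 13 state that the SAP overrides the protocol's statistical considerations. The SAP was written for Amendment 10. Amendment 11 keeps the fixed baseline in 7.2 while sending the analysis to the SAP (Appendix 3), so the two current texts still differ.

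Within the SAP, the listings of tumor size (10.1.2) use both reference points: "Observed values and changes from baseline in relationship to both first and most recent implant will be listed for each study time point". Section 10.1.4 words its listings in the same way. The summary sentences do not. For tumor size the SAP says "at each time point, observed values and changes from baseline will be summarized", and for rating scales "For continuous or discrete outcomes, observed values and changes from baseline will be summarized at each time point". Marker response (10.1.3) is a "decrease from baseline in one or both of CEA or CA 19-9" of at least 20%, again with no baseline named.

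**The concern.** A summary or response rule that refers only to baseline takes its meaning from the section that defines the term. Here that section gives a subject up to four baselines. Any rise between implants then becomes part of the next baseline, and a later fall is measured from the raised level. A subject whose marker is well above its entry value could be recorded as a marker responder. Summarized changes in tumor size, quality of life, pain or performance status after later implants could show one cycle's change instead of change since entry.

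This matters even though SAP 6.2 makes all analyses exploratory. SAP 3.2 says the trial's main focus is to estimate parameters for planning later trials. Protocol 7.1 says the pancreatic data will be used to plan a Phase IIb study, and a marker decrease is one component of the pancreatic primary objective in Protocol 3.2.1. An ambiguous response rate would be carried forward.

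**Working it through.** The plan states no figure on this point, so there is none to reproduce. The check has four steps.

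**1. Which baseline each output names**

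| Output | SAP section | Baseline named |
|---|---|---|
| Tumor size, listing | 10.1.2 | first and most recent implant |
| Tumor size, summary | 10.1.2 | none |
| Rating scales, listing | 10.1.4 | first and most recent implant |
| Rating scales, summary | 10.1.4 | none |
| Marker response | 10.1.3 | none |
| Laboratory summaries (select parameters) and shift tables | 11.1.3 | first and most recent implant |
| ECG summaries | 11.1.5 | first and most recent implant |

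Where the SAP intends a summary against both, it says so: in 11.1.3, "changes from baseline (in relationship to both first and most recent implant) will be summarized for each time point". The outputs that name none can inherit only 6.4.1.2.

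**2. Marker response under each baseline**

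Change = (later value - baseline) / baseline.

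- Marker at 100 on entry, 300 before implant 3, 240 after. Against the latest baseline: (240 - 300)/300 = -20%, a response. Against entry: (240 - 100)/100 = +140%, not a response.
- Marker at 100 on entry, 200 before implant 2, 150 after. Against the latest baseline: (150 - 200)/200 = -25%, a response. Against entry: (150 - 100)/100 = +50%, not a response.
- In general, after a proportional rise r before a later implant, a fall of exactly 20% leaves 0.8 x (1 + r) of the entry value. At r = 0.25 this is 1.00, so the marker is back at entry. At r = 0.875 it is 1.50. That is the 50% increase that Protocol 3.2.2 lists as one of the events making up pancreatic progression.

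After implant 1 the two baselines are the same value, so only subjects with two or more implants can be classified differently.

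**3. Summarized change**

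A lesion measurement growing 30% per cycle shows +30% in each cycle against the latest baseline. Against entry it is 1.3^3 = 2.197 after three cycles, or +120%. Whole-body PET-CT is scheduled at Day 90 of implants 1 to 3 (Protocol 5.1.9, 5.1.14, 5.1.19). That scan would ordinarily be both the outcome of one cycle and the baseline of the next, so the reset makes summarized tumor change essentially per-cycle.

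The effect can also run the other way. A marker that halves after implant 1 and then holds (100, 50, 50) shows 0% in the later cycle against the latest baseline, and -50% against entry.

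**4. Illustration with assumed inputs**

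The documents give no marker variability or growth rate, so these are assumptions: two independent log-normal markers, no treatment effect, a rise of 25% to 100% per 90 days, measurement CV of 10% to 30%, visits at Days 14, 30, 60 and 90, implants 98 days apart, and response taken as any single fall of at least 20% in either marker. Chance of at least one response:

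| Implants | Setting | First baseline | Most recent baseline |
|---|---|---|---|
| 2 | CV 10%, +50% | 5.1% | 7.6% |
| 2 | CV 20%, +50% | 40% | 60% |
| 2 | range over all settings | 2-75% | 3-92% |
| 4 | CV 10%, +50% | 5.1% | 12.5% |
| 4 | CV 20%, +50% | 40% | 83% |
| 4 | range over all settings | 2-76% | 4-99% |

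With one implant the two rates are identical by construction. With more than one, resetting gave the higher rate in every setting, by an amount that depends wholly on the assumptions.

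**The case against.** The strongest reply is that the per-implant reading is inferred. SAP 6.4.1.2 covers implant 1 too and does not say that a later baseline replaces it. In 10.1.2 and 10.1.4 a sentence naming both reference points comes shortly before the summary sentence, and a reader could carry it forward. Section 10.1.3 sends marker reporting to 11.1.3, where changes from both are summarized. Protocol 7.2 concerns the Evaluation Team's response table. SAP section 2 says response parameters were modified, and differences from the protocol are to be explained in the clinical study report. Protocol Appendix 3 asks for efficacy response after one, two, three and/or four implantations, which per-implant baselines can serve. Marker response is not among the listed outcomes and has no table of its own.

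Much of this stands and limits the point. It does not settle the matter. The SAP repeats the dual wording for laboratory and ECG summaries, so its absence elsewhere cannot safely be read as implied. Section 11.1.3 covers select parameters without naming them, and reporting two changes does not say which one makes a subject a responder. An explanation in the study report comes after the results are known.

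A reader might infer that cumulative worsening vanishes from the results. The documents do not support that. Change from the first implant is listed for tumor size and rating scales, and is summarized for select laboratory parameters and for ECG. Observed values are summarized at each time point, and individual marker plots run on a time axis counted from the first implant (6.4.2, 10.1.3).

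**Conclusion.** The point holds in a limited form. The protocol and SAP define baseline differently, and three SAP outputs (marker response, tumor-size summaries and rating-scale summaries) fall by default on the per-implant definition. Followed as written, a marker at 2.4 times its entry value can count as a response, which makes this more than a missing detail.

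It applies only to subjects with two or more implants. The number misclassified cannot be calculated from the documents, and the simulated rates are illustrations only. A reader might infer a general upward bias in the secondary efficacy results. That does not follow: resetting can also hide a sustained benefit, and steady growth still shows as worsening in each cycle. The primary analysis, time from T0 to death, does not use this baseline. The conclusion assumes that an unqualified reference to baseline takes the meaning given in 6.4.1.2.

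**What to change.** In SAP 6.4.1.2 and 10.1.3, state that marker response is judged against the last value before the first implant, as in Protocol 7.2. In 10.1.2 and 10.1.4, make change from that baseline the main efficacy summary and show change from the most recent implant alongside as supportive, matching the dual presentation in 11.1.3. The supportive columns can also serve the sub-analysis by number of implantations.

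The cost is a few sentences of SAP text and some extra table columns. For tumor size and rating scales, both changes are already calculated for the listings. The marker response rate may come out lower.
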